## **6.0 HANDLING OF PATIENT WITHDRAWAL**

Patients may withdraw from the study at any time during the study. Patients may also be withdrawn from the study for not following study related procedures or for the benefit of the patient as determined by study investigators. In the event that a patient withdraws from the study or withdrawn from the study, every attempt should be made to complete the final visit of the study (visit 4 from below). The reason for study discontinuation will be recorded in the subject's folder and case report forms.

All attempts will be made to keep participants in this study. Based on the feasibility aim of this study, the non-compliance guidelines are very lenient. Patients will be withdrawn for non-compliance if they meet any combination of the following: inactivity for 3 consecutive weeks; and/or missing 2 consecutive study appointments where outcome variables are collected.

Patients who discontinue study participation will not be replaced.

In the case study discontinuation is due to an adverse event, such patients will be closely monitored until the resolution or stabilization of this adverse event. This may mean that follow-up will continue after the patient has completed the end of study procedures. Although data on that adverse event will continue to be captured, even beyond the last visit, only those that occur up through the last visit will be recorded.

## 7.0 STUDY PROCEDURES

### 7.1 Visit schedule

Patients will be asked to attend 4 visit with the study investigators. Description of each visit is detailed below.

### 7.2 Pre-screening procedures

Study subjects will be recruited from patients population treated at the University of Texas Health Science Center at San Antonio's Medical Arts and Research Center Urology Clinic. Medical records will be reviewed to determine eligibility. Eligible participants will be mailed recruitment materials and asked to call the investigators if interested in participating in the study. Also, eligible participants will also be approached during regularly scheduled clinic appointments and introduced to the study. Only interested participants will be enrolled into the study.

### 7.3 Description by type of visit

7.3.1 Visit 1 (Baseline Visit) – This will be the first visit in this study and should last about 30-45 minutes. At this session, we will review the consent form, explain the purpose and procedures of the study, ask the subject to sign the consent form if you agree to participate in the study, and randomly assign the subject to one of the two groups mentioned above. Following this, the following things will happen:

1. Assignment of a Nike FitBit – Each participant, no matter which study arm, will be provided with a Nike Fitbit during the 6 month program. The FitBit will monitor activity and will assist the research team in tracking activity and sleep habits. We will instruct subjects on the use and care of the FitBit.
2. Blood Draw –15 mL of blood (two tubes or 1 tablespoon or 3 teaspoons) to measure circulating markers (PSA, PSMA, EPCA, uPA and uPAR) and circulating tumor cells.
3. Saliva Collection – we will collect about 4 mL of saliva (1/4 of a tablespoon or 3/4 teaspoon) to measure FBI concentrations in saliva.
4. Surveys for Quality of Life and Fatigue – subjects will be asked to complete 2 surveys that will take about 5 minutes to complete. These surveys are:
  - a. Health-Related Quality of Life (SF-36) – this survey will assess subject's overall health status, including physical functioning, role functioning, bodily pain, general health, vitality, social functioning, mental health and emotional health.
  - b. Functional Assessment of Chronic Illness – Fatigue (FACIT-F) – This survey evaluates the impact of fatigue in men with prostate cancer.

5. Body Composition, Body Mass Index and Body Density – will measure body fat percentage by measuring skinfold thickness at 3 sites (chest, abdomen, thigh). Body density will be measured using body fat percentage plus the addition of waist and arm circumference. Body mass index will be calculated by collecting by height and weight measurements from the subjects.
6. 6 minute walk test –overall physical function will be measured using the 6 minute walk test. We will track the distance traveled and use this as baseline score.

7.3.2 Visit 2 and Visit 3 (12 week and 18 week visit) – the following activities will be done at the 12 week and 18 week visit:

1. Blood Draw – we will collect 10 mL (2 teaspoons) to measure circulating markers (PSA, PSMA, EPCA, uPA and uPAR). Note: This is different than at baseline and final visit to quantify circulating tumor cells.
2. Download FitBit Data – subjects will be asked to bring the FitBit to this visit so we can download the data that is on the FitBit.
3. Saliva Collection – we will collect about 4 mL of saliva (1/4 of a tablespoon or ¾ teaspoon) to measure FBI concentrations in saliva
4. Body Composition, Body Mass Index and Body Density – will measure body fat percentage by measuring skinfold thickness at 3 sites (chest, abdomen, thigh). We will also measure body mass index by collecting height and weight. Body density will be measured using body fat percentage plus the addition of waist and arm circumference.

7.3.3 Visit 4 (24 week visit; End of Study Visit) – the following activities will be done at the 24 weeks visit (or end of study visit)

1. Blood Draw – we will collect 15 mL of blood (two tubes or 1 tablespoon or 3 teaspoons) to measure circulating markers (PSA, PSMA, EPCA, uPA and uPAR) and circulating tumor cells.
2. Saliva Collection – we will collect about 4 mL of saliva (1/4 of a tablespoon or ¾ teaspoon) to measure FBI concentrations in saliva

3. Surveys for Quality of Life and Fatigue – subjects will be asked to complete 2 surveys that will take about 5 minutes to complete. These surveys are:
  - a. Health-Related Quality of Life (SF-36) – this survey will assess subject's overall health status, including physical functioning, role functioning, bodily pain, general health, vitality, social functioning, mental health and emotional health.
  - b. Functional Assessment of Chronic Illness – Fatigue (FACIT-F) – This survey evaluates the impact of fatigue in men with prostate cancer.
4. Body Composition, Body Mass Index and Body Density – will measure body fat percentage by measuring skinfold thickness at 3 sites (chest, abdomen, thigh). We will also measure body mass index by collecting height and weight. Body density will be measured using body fat percentage plus the addition of waist and arm circumference.
5. 6 minute walk test – we measure overall physical function by asking subjects to walk for 6 minutes. We will track the distance traveled and use this as the post-intervention score.
6. Return Nike FitBit – subjects will be asked to return the Nike FitBit to the research team. Data from the FitBit will be downloaded. After downloading, all data that is on the FitBit will be erased. A summary of the subject's activity can be provided if desired.

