## **5.0 DESCRIPTION OF INTERVENTION**

**5.1 Home-based exercise program.** The intervention will include a combination of both aerobic and body-weight based exercises. The aerobic portion of the intervention will include 5 days of light to moderate intensity walking for 30 mins (weekly total of 150 mins). Intensity will be set at 40-60% of the individual's heart rate reserve using the Karvonen formula (Exercise HR = % of target intensity ( $HR_{max} - HR_{rest}$ ) +  $HR_{rest}$ ). Participants

will be given their targeted HR range by the PI and will be taught how to palpate and calculate HR prior to the beginning of the program. The body-weight based exercises will be done 3 times a week. Exercises will consist of 3 sets of 15 reps of bodyweight squats, incline push-ups, and hip thrusts. If these exercises cannot be performed, lower intensity exercises such as sit-to-stand, wall push up and pelvic tilt can be replaced. These exercises are aimed at increasing strength and endurance of the major muscle groups of the body. Individuals in this group will be given a pocket guide with instructions on how to safely perform the exercises and document the completion of the exercises.

**5.2 Waitlist-Control Group.** Participants assigned to this group will be asked to maintain normal activity and visit the CTRC fitness center for research appointments.

**5.3 Method of assigning patients to intervention group.** Patients eligible to participate in this study will be allocated to either the exercise group or wait-list control group (1:1) based on a pre-specified randomization list

Example:

**Set #1:** 2, 1, 2, 2, 1, 2, 2, 2, 1, 1, 2, 2, 2, 1, 2, 1, 2, 2, 2, 1, 1, 1, 1, 2, 2, 1, 2, 1, 2, 2

1: Control Group; 2: Intervention Group

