## **8.0 STATISTICAL CONSIDERATIONS**

### **8.1 Statistical analysis plan**

Analysis will be done after all participants have completed the 12-week and 24-week timepoints, respectively. The interim analysis at 12-weeks will be for safety and efficacy of the intervention and will include a between group comparison of circulating biomarkers and a review of adverse events reported by study participants.

Statistical analysis will be performed using IBM SPSS 19.0 software. A 2 group analysis of variance (ANOVA) will be used to compare changes in biomarkers, physical function, body composition, body density, and quality of life between the exercise group and the WLC. Pearson's Product Moment Correlation will be used to measure associations between biomarkers in Aim 1 to body composition, body density, physical function and quality of life measured in aim 2. A value of  $p < 0.05$  will be considered statistically significant. The results of this study will be used to calculate power and determine sample size for future research questions in this field.

We will also evaluate the projects procedures and timeline for feasibility. We will document and review our timelines for recruitment for this pilot and ask participants to comment on their experiences in this project with pointed efforts to understand ways to improve the project procedures for effectiveness and efficiency. We will also assess feasibility by documenting and reviewing study patient description described below.

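### Men are randomised before any baseline measure is taken, so the baseline 6-minute walk, SF-36 and FACIT-F may be coloured by knowledge of the arm and carry that into the change comparison

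*Combined protocol and SAP*

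**What the plan says.** Section 7.1 sets four visits: "Patients will be asked to attend 4 visit with the study investigators". Section 7.3.1 says of Visit 1: "This will be the first visit in this study and should last about 30-45 minutes". No earlier visit exists at which a baseline could be taken.

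Within Visit 1 the order is explicit. After consent, staff are to "randomly assign the subject to one of the two groups mentioned above. Following this, the following things will happen". The numbered list is then FitBit, blood, saliva, the two surveys (SF-36 and FACIT-F), body composition and the 6-minute walk. For the walk the text adds: "We will track the distance traveled and use this as baseline score".

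The walk and the surveys are not listed for weeks 12 and 18 (section 7.3.2). They return only at week 24 (section 7.3.3), where the walk entry reads "We will track the distance traveled and use this as the post-intervention score".

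Section 8.1 uses a two-group ANOVA "to compare changes in biomarkers, physical function, body composition, body density, and quality of life". It names no baseline covariate.

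On allocation, section 5.3 gives only a pre-specified 1:1 list. No section describes masking of participants or assessors, or a delay in telling a man his arm. The one statement on timing is in section 5.1, where the exercise participants "will be taught how to palpate and calculate HR prior to the beginning of the program".

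**The concern.** A baseline should be a measurement that assignment cannot have influenced. Here every baseline value follows assignment. This matters little for an assay, but the walk depends on effort and the surveys are self-reports. A man who has just learned that he will exercise, or that he must wait, may walk or answer differently. The direction cannot be predicted.

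The walk and the surveys each have one baseline and one follow-up value, so their result rests wholly on this post-assignment measurement. The walk is the named measure of physical function in objective 2.3.1, whose hypothesis is a significant improvement over control. Section 8.1 also states: "The results of this study will be used to calculate power and determine sample size for future research questions in this field". A shifted walk or survey difference would carry forward if it were used for that purpose.

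There is a secondary consequence. A man who leaves after learning his arm but before the measures is randomised with no baseline. Section 6 does not replace him, section 8.4 includes all randomised patients in the primary analysis, and he can contribute no change score.

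**Working it through.** **What is stated and what is inferred.** Stated: assignment precedes all baseline measures, the walk and surveys occur only at Visits 1 and 4, and changes are compared. Inferred: men know their arm when they walk and answer. The arms are plain to participants once disclosed, because one receives a heart-rate range and a pocket guide (5.1) and the other is asked to keep to normal activity (5.2). The moment of disclosure is not given.

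**Inputs from the documents.** 15 men per arm (4.1), so 28 degrees of freedom; significance at p < 0.05 (8.1). The F test in a two-group ANOVA is equivalent to a two-sided t test. The plan gives no effect size, SD or power, so there is no figure to reproduce.

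**Assumptions, for illustration only.** Outcome SD is 1 at both visits. The baseline-to-week-24 correlation r is 0.5, 0.7 or 0.8. Let b0 and b24 be the exercise-minus-control shifts, in SD, that knowing the arm causes at baseline and at week 24.

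**Bias in the difference in change.**
- Present order: b24 − b0.
- Measures before allocation: b24, because b0 is then zero by design.

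| b0 | b24 | Absolute bias, present order | Absolute bias, reordered |
|---|---|---|---|
| +0.2 | 0 | 0.2 | 0 |
| +0.2 | 0.1 | 0.1 | 0.1 |
| +0.2 | 0.2 | 0 | 0.2 |
| −0.2 | 0 | 0.2 | 0 |
| −0.2 | 0.1 | 0.3 | 0.1 |
| −0.2 | 0.2 | 0.4 | 0.2 |

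Reordering reduces the absolute bias when b0 has the opposite sign to b24 or is more than twice its size. When the two have the same sign and b0 is less than twice b24, they partly or wholly cancel in the present order, and reordering leaves a larger bias.

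**From bias to false-positive rate, with no true effect.**
- Var(change) = 2(1 − r) = 1.0, 0.6, 0.4 for r = 0.5, 0.7, 0.8.
- SE of the between-arm difference = √((2/15) × Var) = 0.365, 0.283, 0.231.
- Noncentrality = bias / SE. For a bias of 0.2 this is 0.55, 0.71, 0.87.
- The rejection rate follows from the noncentral t distribution with 28 degrees of freedom.

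| Absolute bias (SD) | r = 0.5 | r = 0.7 | r = 0.8 |
|---|---|---|---|
| 0 | 0.050 | 0.050 | 0.050 |
| 0.1 | 0.058 | 0.063 | 0.070 |
| 0.2 | 0.083 | 0.105 | 0.133 |
| 0.3 | 0.125 | 0.176 | 0.241 |
| 0.4 | 0.185 | 0.277 | 0.387 |

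Simulation with 100,000 trials per case agrees: b0 = 0.2 with b24 = 0 gives 0.084 (r = 0.5) and 0.132 (r = 0.8); b0 = −0.2 with b24 = 0.1 gives 0.125 and 0.240.

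**Would baseline adjustment repair it?** No. With ANCOVA the baseline shift enters multiplied by r. At r = 0.7 and b24 = 0, a shift of 0.2 SD leaves 0.7 × 0.2 = 0.14 SD of bias and a false-positive rate of about 0.081, against 0.105 for the change score.

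**The case against.** Several points on the other side have force.

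- *Disclosure at assignment is not documented.* This is true, and the link from order to bias is an inference. Within one short visit, before any exercise, only an expectation effect is in play. But nothing in the plan prevents disclosure at that point, and the silence is itself a reason to settle the text.
- *The reach is small.* This stands. The primary blood markers and the salivary marker are not materially affected. Skinfolds are at risk only if the assessor knows the arm, which is not documented. That leaves an objective in the Other category and two surveys. Section 2 lists no quality-of-life objective, although 8.1 mentions quality of life as measured in an aim 2. Section 8.1 also does not say that the walk or surveys will size a later trial.
- *Reordering does not always help.* This also stands. In the six cases above it helps in four, changes nothing in one and does worse in one. With b0 = +0.2 and b24 = 0.3, outside that grid, the bias goes from 0.1 to 0.3. The highest rates, 0.185 to 0.387, need opposite shifts of 0.2 at each visit, and half of that bias remains after reordering (0.083 to 0.133). Still, two unknown biases that happen to cancel are no reason to keep one of them.

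These points limit how much the change can be claimed to achieve. They do not make the present order preferable.

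**Conclusion.** The concern holds. Section 7.3.1 puts every baseline measure after randomisation, and no safeguard is described. For the walk, SF-36 and FACIT-F, any arm-related baseline shift passes in full into the between-arm difference in change. Its size and direction are unknown; the false-positive rates above rest wholly on assumed shifts and correlations.

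The change is worth making but is not critical, because it leaves the primary and secondary marker comparisons essentially untouched. Confidence is moderate, since the time at which men learn their arm is inferred.

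**What to change.** Reorder section 7.3.1:

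1. After consent is signed, complete items 2 to 6: blood, saliva, SF-36 and FACIT-F, body composition, 6-minute walk.
2. Only then take the next allocation from the section 5.3 list and disclose it.
3. Then issue the FitBit (item 1) and, for the exercise group, give the exercise instruction.

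Define baseline as values obtained before randomisation. Eligibility stays with the record review in section 7.2. State as a limitation that the week-24 walk and surveys remain open-label, so a bias of b24 is still possible. For any men already enrolled, report the order actually followed.

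The cost is small: an amendment to the wording of 7.3.1, its handling by the IRB (with the consent text checked if it describes the order), and the report to the research team that section 9.1.2 requires. The visit, staff, assessments and randomisation list stay the same.

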## 7.4 Sample Processing

### 7.4.1 Serum Processing

Whole blood will be collected through the antecubital vein in the non-dominant arm into a red topped vacutainer with clot activator. After inverting 3-5 times to ensure proper mixing, samples will be centrifuged at 2,000 x g for 15 minutes. Serum will be aliquoted in .5 mL samples and stored in a -80C freezer until analysis.

### 7.4.2 Saliva Processing

Raw saliva samples (~4 ml) will be collected by passive drooling into two 2mL tubes. Within 30 minutes of collection that sample is placed in a -80C freezer. After the completion of each time point, one 2mL tube for each participant will be transported to the Hyperion laboratory located at [name] and stored at -80C until analysis.

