**1.2 Biomarker for Cancer-related Fatigue.** Prostate cancer survivors commonly report having 1 or more cancer related symptom that impacts their quality of life. One common symptom associated with cancer, termed cancer-related fatigue, is exceedingly common and treatable not only in prostate cancer patients but other cancers as well. Cancer-related fatigue is reported by 50-90% of patients as a symptom of their cancer [4]. Patients report fatigue as one of the most important and distressing symptoms related to cancer and its treatment and is a strong predictor of clinical patient satisfaction as well as patient quality of life. Measurement of fatigue in PCa has typically come in the form of paper-based surveys. Opportunities exist for advancing the field with novel methods of assessing fatigue in this clinical population. Biomarkers would provide an objective method to track a patient's fatigue level during treatment, allowing clinicians to optimize treatment with respect to the patient's fatigue level. In previous studies, our collaborators at Hyperion Biotechnology identified a salivary biomarker of physical fatigue, called the Fatigue Biomarker Index (FBI) and demonstrated the utility of this marker in predicting the outcome of physically demanding military training. Using a similar approach to biomarker discovery, the same collaborators have also identified a salivary biomarker candidate for chronic fatigue syndrome. Both of these salivary biomarkers are based on changes in levels of naturally occurring peptide fragments arising from the same family of salivary proteins, the salivary Proline –rich Proteins (PRPs). Others have also identified changes in the levels of similar salivary peptides in Sjogren's syndrome, a disease associated with significant fatigue. Taken together, these finds suggest a fundamental physiological link between a person's fatigue level and the composition of the individual's saliva. Investigating whether similar changes in saliva are associated with fatigue is justified.

**1.3 Survey measurements for quality of life.** Quality of life will be measured using the Short-Form-36 and the Functional Assessment of Chronic Illness Therapy-Fatigue surveys.

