## **2.0 STUDY OBJECTIVES**

**2.1 Primary Objective:** To demonstrate the impact of a home based exercise program versus wait-list control to modulate circulating prognostic biomarkers PSA, PSMA, EPCA, uPA and uPAR in men with prostate cancer under active surveillance..

2.1.1 Hypothesis: The home based exercise program participants will have significantly lower concentrations of circulating biomarkers compared to their non-exercising counterparts.

**2.2 Secondary Objective:** To determine the impact of a home based exercise program versus wait-list control to modulate a novel salivary biomarker for fatigue in men with prostate cancer under active surveillance.

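### Saliva for the fatigue marker is sampled with no standard interval since the last exercise session, although only one arm has scheduled sessions, so recent exertion can differ by arm and enter the comparison

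*Combined protocol and SAP*

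**What the plan says.** - **The outcome.** Section 2.2 makes the salivary marker the secondary objective: "To determine the impact of a home based exercise program versus wait-list control to modulate a novel salivary biomarker for fatigue". Section 7.3 names FBI as what is measured in saliva. Section 1.2 says that the collaborators "identified a salivary biomarker of physical fatigue, called the Fatigue Biomarker Index (FBI").
- **The exercise arm.** Under section 5.1 the aerobic part "will include 5 days of light to moderate intensity walking for 30 mins". In addition, "The body-weight based exercises will be done 3 times a week". The section does not say whether the body-weight work shares days with the walking.
- **The control arm.** Section 5.2: "Participants assigned to this group will be asked to maintain normal activity".
- **Sampling.** Saliva is taken at baseline and at weeks 12, 18 and 24 (section 7.3). Section 7.4.2 gives method and volume: "Raw saliva samples (~4 ml) will be collected by passive drooling into two 2mL tubes". Its only time limit applies after collection: "Within 30 minutes of collection that sample is placed in a -80C freezer". Section 8.3 allows one week around each scheduled visit. No section sets an interval since exercise or asks for the last session to be noted at sampling.
- **Analysis.** Section 8.1 compares changes in biomarkers between arms by a two-group ANOVA at p < 0.05, with no term for recent exertion.
- **Activity records.** Both arms wear a FitBit, with data downloaded at weeks 12, 18 and 24 (section 7.3). Exercise-arm men log completed exercises in a pocket guide (section 5.1). Neither record is tied to the time of sampling.

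**The concern.** The secondary objective asks whether a 24-week programme changes a fatigue marker. A marker of physical fatigue taken soon after a session may partly reflect that session and not the programme's lasting effect. Both arms attend the same visits, but only one has a schedule that places sessions near them. Exposure to recent exertion is thus a consequence of allocation: randomisation does not balance it, and averaging over more men or visits does not remove it.

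Subtracting baseline does not help either. At visit 1 the man consents, is randomised and is sampled in one appointment, before any programme session. Any acute effect would therefore be in the follow-up value and absent from the baseline value.

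At stake is the interpretation of the FBI comparison. Section 8.1 also intends the results to inform power and sample size for later studies, so a distorted estimate would be carried forward. Once samples are frozen, the interval can no longer be standardised.

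**Working it through.** The plan states no effect size, SD or power for FBI, so there is no planned figure to reproduce. The check is a reading of the sampling and analysis text, followed by an illustration of scale.

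**Step 1: does any rule control time since exercise?** Sections 7.3, 7.4.1 and 7.4.2 cover volumes, vein, tube, spin, freezing and storage. Section 8.3 gives a calendar window. Section 8.1 has no covariate. No rule was found.

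**Step 2: share of exercise-arm samples on a walking day.** Assume visits fall at random in the week and the prescription is followed. With walking on 5 of 7 days, 5/7 = 0.714, or 71%. If body-weight sessions fell on both non-walking days, which section 5.1 does not exclude, every day would be an exercise day (100%). As a low case, take 3/7 = 43%.

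**Step 3: bias.** In SD units of the change score, bias = share affected × acute shift. The shift is not in the documents, so a range is assumed. Controls are taken as unaffected.

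- 0.714 × 0.25 = 0.18 SD
- 0.714 × 0.50 = 0.36 SD

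**Step 4: yardstick.** With 15 per arm (section 4.1), all analysed, and a two-sided 5% test (sidedness is not stated), the smallest significant difference is t(0.975, 28 df) × √(2/15) = 2.048 × 0.365 = 0.748 SD. The bias above is 0.18/0.748 = 24% to 0.36/0.748 = 48% of that.

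**Step 5: chance of p < 0.05 with no true programme effect.** Two-sided noncentral t, 28 df, noncentrality = bias × √(15/2), ignoring the extra spread from a partly affected arm:

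| Assumed shift | 3/7 affected | 5/7 affected | All affected |
|---|---|---|---|
| 0 | 5.0% | 5.0% | 5.0% |
| 0.25 SD | 5.9% (bias 0.11) | 7.6% (bias 0.18) | 10.1% (bias 0.25) |
| 0.5 SD | 8.8% (bias 0.21) | 15.7% (bias 0.36) | 26.2% (bias 0.50) |
| 1.0 SD | 20.5% (bias 0.43) | 47.2% (bias 0.71) | 75.3% (bias 1.00) |

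The table shows how the result depends on the unknown shift. It does not estimate that shift.

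**The case against.** **No acute response is documented.** Section 1.2 does not say that FBI moves after a session, by how much, in which direction or for how long. It reports that the marker helped to predict the outcome of strenuous military training, and it cites related salivary peptides in chronic fatigue syndrome and Sjogren's syndrome, which are lasting conditions. The prescription here is walking at 40-60% of heart rate reserve plus body-weight work. This stands: a reader might infer that arm-related bias is to be expected, or that an acute rise would hide or reverse a benefit, but the text supports neither. It does not say which direction of FBI means more fatigue.

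**Controls may exercise too.** This stands. Normal activity can include walking. What differs by arm is the scheduled sessions, not all exertion.

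**Activity is already recorded.** This stands in part. The FitBit and the pocket guide could date recent exertion, so it would be wrong to say that nothing is recorded. But the plan does not use them for this, and a record alone does not make the arms comparable at sampling.

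**The 71% is rough.** This stands. It counts days, not samples taken after a session, and a session later the same day cannot affect a sample. It also assumes full adherence, which section 8.2 sets out to assess. In the other direction, it leaves out sessions on the previous day and body-weight work on non-walking days.

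**It is a pilot and the outcome is secondary.** That limits the weight of the point. It does not remove a gap that is cheap to close only before sampling.

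**Conclusion.** The point holds for saliva, as a possible bias that a simple sampling instruction would guard against. Following the plan as written leaves exposure to recent scheduled exertion different by arm, and a change from a pre-programme baseline cannot remove its effect.

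The size is unknown. Under an assumed shift of 0.25 to 0.5 SD in 5/7 of exercise-arm samples, with controls unaffected, the bias would be about a quarter to a half of the difference needed for significance. With no acute response the test keeps its 5% level.

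A reader might extend the argument to PSA, PSMA, EPCA, uPA and uPAR, since the blood draw has no interval rule either. The documents do not support that: nothing in them says that these markers respond to acute exertion. For blood, only the absence of a rule is established.

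**What to change.** - **Sections 7.3 and 7.4.2:** give both arms the same instruction at every visit, including baseline, to leave a minimum interval without an exercise session before saliva sampling. The sponsor should choose the length. Booking visits on an exercise-free day is not a substitute: section 5.1 does not guarantee such a day, and a visit on one could still closely follow a session the evening before.
- **Case report form:** record the time of sampling and the time of the last session, checked against the FitBit data in both arms and the pocket guide in the exercise arm.
- **Section 8.1:** add a sensitivity analysis of FBI that accounts for time since the last session. Simply excluding samples that miss the interval could remove mostly exercise-arm data from 15 men, so it should not be the only approach. This analysis supports the instruction and does not replace it.

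The same instruction can cover the blood draw at no extra cost, as good practice and not as the remedy for a demonstrated bias.

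The cost is slightly less flexible booking and two recorded times per visit.
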